### Section C-3.9 Incidence rate of self-reported anemia

Table C-3.9.1 Incidence rate of self-reported anemia, AT population, Complete cohort

	DNG		OAED			NAED		Ex-use	Allocation unknown	Total
		GnRH-a	Danazol	All OAED	CC	Other progestin	All NAED			
Number of women years	xx	xx	xx	XX	xx	xx	xx	xx	xx	xx
Self-reported anemia	xx	xx	xx	xx	xx	xx	xx	xx	xx	xx
IR* (95% CI)	xx.x (xx.x-x.x)	xx.x (xx.x-x.x)	xx.x (xx.x-x.x)	xx.x (xx.x-x.x)	xx.x (xx.x-x.x)					
Thereof										
Confirmed	xx	xx	xx	xx	xx	xx	xx	xx	xx	xx
	xx.x (xx.x-x.x)	xx.x (xx.x-x.x)	xx.x (xx.x-x.x)	xx.x (xx.x-x.x)	xx.x (xx.x-x.x)					
Not confirmed	XX	XX	xx	xx	xx	xx	XX	xx	xx	xx
	xx.x (xx.x-x.x)	xx.x (xx.x-x.x)	xx.x (xx.x-x.x)	xx.x (xx.x-x.x)	xx.x (xx.x-x.x)					
Thereof										
Recurrent anemia	xx	XX	xx	xx	XX	xx	XX	xx	xx	xx
	xx.x (xx.x-x.x)	xx.x (xx.x-x.x)	xx.x (xx.x-x.x)	xx.x (xx.x-x.x)	xx.x (xx.x-x.x)					
Potential anemia,	xx	xx	xx	xx	xx	xx	xx	xx	xx	xx
no further clarification possible	xx.x (xx.x–x.x)	xx.x (xx.x–x.x)	xx.x (xx.x–x.x)	xx.x (xx.x-x.x)	xx.x (xx.x-x.x)	xx.x (xx.x–x.x)	xx.x (xx.x–x.x)	xx.x (xx.x-x.x)	xx.x (xx.x–x.x)	xx.x (xx.x–x.x)
Anemia caused by	XX	xx	xx	XX	XX	xx	XX	xx	xx	xx
other reason**	xx.x (xx.x-x.x)	xx.x (xx.x-x.x)	xx.x (xx.x-x.x)	xx.x (xx.x-x.x)	xx.x (xx.x-x.x)					
Anemia not confirmed	XX	xx	xx	xx	XX	xx	XX	xx	xx	xx
by diagnostic measures	xx.x (xx.x-x.x)	xx.x (xx.x-x.x)	xx.x (xx.x-x.x)	xx.x (xx.x-x.x)	xx.x (xx.x-x.x)					
Anemia not treated by	XX	xx	xx	xx	XX	xx	XX	xx	xx	xx
НСР	xx.x (xx.x-x.x)	xx.x (xx.x-x.x)	xx.x (xx.x-x.x)	xx.x (xx.x-x.x)	xx.x (xx.x-x.x)					
"No event" - before	xx	xx	xx	xx	xx	xx	xx	xx	xx	xx
study, repetition	xx.x (xx.x-x.x)	xx.x (xx.x-x.x)	xx.x (xx.x-x.x)	xx.x (xx.x-x.x)	xx.x (xx.x-x.x)					

Note: \* Incidence rate is shown per 10^4 women years.

Note: \*\* Includes e.g. other primary disease, surgery

Supporting document SOP BMT 01.09 – Doc 5002.02 – Effective date 21.03.2017

Table C-3.9.2	Incidence rate of self-reported anemia, AT population, Starter
Table C-3.9.3	Incidence rate of self-reported anemia, AT population, Switcher
Table C-3.9.4	Incidence rate of self-reported anemia, AT population, Restarter
Table C-3.9.5	Incidence rate of self-reported anemia, AT population, Diagnosis confirmed by surgery
Table C-3.9.6	Incidence rate of self-reported anemia, AT population, Diagnosis based on clinical symptoms
Table C-3.9.7	Incidence rate of self-reported anemia, AT population, Germany
Table C-3.9.8	Incidence rate of self-reported anemia, AT population, Poland
Table C-3.9.9	Incidence rate of self-reported anemia, AT population, Hungary
Table C-3.9.10	Incidence rate of self-reported anemia, AT population, Switzerland
Table C-3.9.11	Incidence rate of self-reported anemia, AT population, Russia
Table C-3.9.12	Incidence rate of self-reported anemia, AT population, Ukraine

Supporting document SOP BMT 01.09 – Doc 5002.02 – Effective date 21.03.2017

### Section C-3.10 Incidence rate of self-reported depression

Table C-3.10.1 Incidence rate of self-reported depression, AT population, Compete cohort

	DNG		OAED			NAED		Allocation unknown	Total
		GnRH-a	Danazol	All OAED	СС	Other progestin	All NAED		
Number of women years	xx	xx	xx	xx	xx	xx	xx	xx	xx
Self-reported depression	xx	xx	xx	XX	xx	xx	XX	xx	XX
IR* (95% CI)	xx.x (xx.x-x.x)	xx.x (xx.x-x.x)	xx.x (xx.x-x.x)	xx.x (xx.x–x.x)					
Thereof									
Confirmed	xx	xx	xx	xx	xx	xx	xx	xx	XX
	xx.x (xx.x-x.x)	xx.x (xx.x-x.x)	xx.x (xx.x-x.x)	xx.x (xx.x-x.x)					
Not confirmed	xx	xx	xx	xx	xx	xx	xx	xx	XX
	xx.x (xx.x-x.x)	xx.x (xx.x-x.x)	xx.x (xx.x-x.x)	xx.x (xx.x-x.x					
Thereof									
Recurrent depression	xx	xx	xx	xx	xx	xx	xx	xx	XX
	xx.x (xx.x-x.x)	xx.x (xx.x-x.x)	xx.x (xx.x-x.x)	xx.x (xx.x-x.x)					
Potential depression,	xx	xx	xx	xx	xx	xx	xx	xx	XX
no further clarification	xx.x (xx.x-x.x)	xx.x (xx.x-x.x)	xx.x (xx.x-x.x)	xx.x (xx.x-x.x)					
possible									
Depression treated by	xx	xx	xx	XX	XX	xx	xx	XX	XX
GP	xx.x (xx.x-x.x)	xx.x (xx.x-x.x)	xx.x (xx.x-x.x)	xx.x (xx.x-x.x)					
Depressive disorders	XX	xx	xx	XX	XX	XX	XX	XX	XX
treated by psychologist	xx.x (xx.x-x.x)	xx.x (xx.x-x.x)	xx.x (xx.x-x.x)	xx.x (xx.x-x.x)					
Other psychiatric	XX	xx	xx	XX	XX	XX	XX	XX	XX
disorders**	xx.x (xx.x-x.x)	xx.x (xx.x-x.x)	xx.x (xx.x-x.x)	xx.x (xx.x-x.x)					
Other psychic	xx	xx	xx	XX	XX	xx	xx	xx	xx
problems***	xx.x (xx.x-x.x)	xx.x (xx.x-x.x)	xx.x (xx.x-x.x)	xx.x (xx.x-x.x)					
"No event" - before	xx	xx	XX	xx	xx	xx	xx	xx	xx
study, repetition	xx.x (xx.x-x.x)	xx.x (xx.x-x.x)	xx.x (xx.x-x.x)	xx.x (xx.x-x.x)					

Supporting document SOP BMT 01.09 – Doc 5002.02 – Effective date 21.03.2017

Note: \* Incidence rate is shown per 10^4 women years.

Note: \*\* Includes e.g. schizophrenia, bipolar, anxiety, eating disorders.

Note: \*\*\* Includes e.g. mood changes, psychosomatic disorders, no HCP visited.

Table C-3.10.2 Incidence rate of self-reported depression, AT population, Starter
Table C-3.10.3 Incidence rate of self-reported depression, AT population, Switcher
Table C-3.10.4 Incidence rate of self-reported depression, AT population, Restarter
Table C-3.10.5 Incidence rate of self-reported depression, AT population, Diagnosis confirmed by surgery
Table C-3.10.6 Incidence rate of self-reported depression, AT population, Diagnosis based on clinical symptoms
Table C-3.10.7 Incidence rate of self-reported depression, AT population, Germany
Table C-3.10.8 Incidence rate of self-reported depression, AT population, Poland
Table C-3.10.9 Incidence rate of self-reported depression, AT population, Hungary
Table C-3.10.10 Incidence rate of self-reported depression, AT population, Switzerland
Table C-3.10.11 Incidence rate of self-reported depression, AT population, Russia
Table C-3.10.12 Incidence rate of self-reported depression, AT population, Ukraine

Supporting document SOP BMT 01.09 - Doc 5002.02 - Effective date 21.03.2017

### Section D Comparisons and Inferential Statistics of Primary Outcomes

#### Section D-1 New anemia and reoccurrence of anemia

Table D-1.1.1 Incidence rate ratio of new anemia and reoccurrence of anemia between EMT user cohorts, AT population

Comparison	Cohort	No. of	WY	Incidence	Incidence Rate Ratio
Group		events		rate*	(95% CI)
	DNG	xx	xxxxx	x.xxxx	x.xxxx
1	OAED	xx	xxxxx	x.xxxx	(x.xxxx - x.xxxx)
2	DNG NAED	xx xx	xxxxx	x.xxxx x.xxxx	x.xxxx (x.xxxx - x.xxxx)
2	DNG	xx	xxxxx	x.xxxx	x.xxxx
3	Ex-use	XX	xxxxx	x.xxxx	(x.xxxx - x.xxxx)

Note: \*Incidence rate per 10^4 women years

Supporting document SOP BMT 01.09 – Doc 5002.02 – Effective date 21.03.2017

Table D-1.1.2 Risk of new anemia and reoccurrence of anemia obtained from Cox model (HR), AT population

Cohort	No. of	No. of WYs		Hazard Ratio (95% CI)		
	events			Crude HR	Adjusted HR	
DNG	xx	xxxxx	x.xxxx	x.xxxx	x.xxxx	
OAED	XX	xxxxx	x.xxxx	(x.xxxx - x.xxxx)	(x.xxxx - x.xxxx)	
DNG	xx	xxxxx	x xxxx	x xxxx	X.XXXX	
NAED	xx	xxxxx	x.xxxx	(x.xxxx - x.xxxx)	(x.xxxx - x.xxxx)	
DNG	VV		V VVVV	V VVVV	V	
Ex-use	xx xx	XXXXX	x.xxxx x.xxxx	x.xxxx (x.xxxx - x.xxxx)	x.xxxx (x.xxxx - x.xxxx)	
	DNG OAED  DNG NAED	DNG XX DNG XX DNG XX DNG XX NAED XX	DNG XX XXXXX  DNG XX XXXXX  DNG XX XXXXX  DNG XX XXXXX  DNG XX XXXXX	DNG XX XXXXX X.XXXX OAED XX XXXXX X.XXXX  DNG XX XXXXX X.XXXX  NAED XX XXXXX X.XXXX  DNG XX XXXXX X.XXXX	DNG     XX     XXXXXX     XXXXXX     XXXXXX       OAED     XX     XXXXXX     XXXXXX     XXXXXX       DNG     XX     XXXXXX     XXXXXX     XXXXXX       NAED     XX     XXXXXX     XXXXXX     XXXXXX       DNG     XX     XXXXXX     XXXXXX     XXXXXX	

Note: \*Adjusted for age, history of bleeding and history of anemia.

Section D-2	New depression or deterioration of existing depression
	Incidence rate ratio of new depression or deterioration of existing depression between EMT user cohorts, AT population Risk of new depression or deterioration of existing depression obtained from the Cox model (HR), AT population
Section D-3	Treatment failure
Section D-3.1	Incidence rate ratio of treatment failure between EMT user cohorts, AT population
Section D-3.2	Risk of treatment failure obtained from the Cox model (HR), AT population

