#### 5.3.2 Stratifying factors

The numbers of patients enrolled and included in the analysis populations will be tabulated by defined stratifying variables for the AT and ITT population, if appropriate.

Baseline and follow-up population characteristics will be presented for the AT and ITT population and stratified by

Supporting document SOP BMT 01.09 – Doc 5002.02 – Effective date 21.03.2017

- (1) Country
- (2) EMT user type: starter vs. switcher vs. restarter
- (3) Diagnostic classification: Diagnosis confirmed by surgery vs. diagnosis based on clinical symptoms,

if not otherwise specified.

The analysis of the primary and secondary outcomes will be presented for the AT population, anemia and depression additionally for the ITT population. Primary and secondary outcomes are stratified by subgroups if appropriate:

- (1) Country
- (2) EMT user type: starter vs. switcher vs. restarter
- (3) Diagnostic classification: Diagnosis confirmed by surgery vs. diagnosis based on clinical symptoms

Selected outcomes regarding the baseline risk (lifetime history of co-morbidity, risk markers, co-medication, socio-demographic and lifestyle data), will be additionally displayed by subgroups as follows:

- (1) Age categories: < 20 vs. 20 to < 30 vs. 30 to < 40 vs. >= 40
- (2) Age standardized

Additional subgroups will be added for selected outcomes if appropriate.

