#### 5.4.2 Regression models

Regression analysis will be performed if a sufficient number of confirmed events are available for estimation, i.e. n≥5 confirmed events in each of the comparison groups.

Potential confounders such as

- age, personal and family history of depression, history of anemia, history of bleeding disorders and severity of pain will be included as time-invariant cofactors.
- EMT user type at follow up, use of Antidepressants/SSRI and current or worsening depression (primary outcome) will be included as time-dependent cofactors.

For each primary outcome, a summary table with predefined potential prognostic factors and the corresponding relative risk estimators is provided.

The final decision on the confounding variables will be made by the Safety Monitoring and Advisory Council:

Primary outcome variable	Predefined Prognostic Factors 	
Anemia	Age, history of anemia, history of bleeding disorders	
Depression	Age, family and personal history of depression, use of Antidepressants/SSRI	
Treatment Failure	Age, family and personal history of depression, severity of pain	

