#### Section C - Clinical Outcome

Section C provides incidence rates of primary (Section C1), secondary (Section C2) and safety outcomes (Section C3) and other outcomes of interest (Section C4).

Section C-1 Primary outcomes

The analysis of the primary outcomes (Section C1) is stratified by country, EMT user type and diagnosis classification.

Anemia

Incidence rate of Anemia

Depression

Incidence rate of Depression

Treatment failure

Incidence proportion of treatment failure

Section C-2 Secondary Outcomes

The analysis of the secondary outcomes (Section C2) is stratified by country, EMT user type and diagnosis classification.

Supporting document SOP BMT 01.09 – Doc 5002.02 – Effective date 21.03.2017

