## 10. Appendix

### I Baseline questionnaire

#### **INAS-VIPOS**

International Active Surveillance Study of Medication Used for the Treatment of Endometriosis:  $\underline{V} is anne \ \underline{P} ost-approval \ \underline{O} bservational \ \underline{S} tudy$ 

	- Baseline Questionnaire -
	Country Physician no. Patient no. ID
If you	have any questions, please call our toll-free number: [telephone number].
	To be filled in by the physician!
1.	What is the name of the medication for endometriosis that you prescribed to your patient today?,
1a.	If you prescribed an oral contraceptive today, have you prescribed an extended regimen? 2
	□ No □ Yes
2.	Please tick the appropriate box to describe today's prescription: 3
	☐ First-time hormonal prescription/no previous hormonal treatment
	☐ Repeat of the same hormonal treatment after a medication break of at least 4 weeks
	☐ Switching from another hormonal treatment without a relevant break (< 4 weeks)
	☐ Switching from another hormonal treatment after a break of at least 4 weeks
3.	How would you classify your patient's endometriosis? 4
	□ Diagnosis based only on clinical symptoms
	☐ Endometriosis confirmed via surgery / laparoscopy
4.	In the last 2 years, how many surgical procedures (diagnostic and/or therapeutical) has your patient received for the management of her endometriosis?
	Number of surgical procedures:
	To be filled in by the study participant!
Pers	onal Data
5.	Please give your date of birth: $\bigcup_{\text{day}}^{\square} \bigcup_{0}^{\square} \bigcup_{\text{month}}^{\square} \bigcup_{\text{year}}^{\square} \bigcup_{\text{year}}^{\square} \bigcup_{0}^{\square} \bigcup_{0}^{\square} \bigcup_{\text{year}}^{\square} \bigcup_{0}^{\square} \bigcup_{0}^{$
6.	What is your height?, cm
7.	What is your weight?kg
Gyn	ecological History
8.	How old were you when you had your first menstrual bleeding?
9.	Have you ever been pregnant? 12
	□ No → go to question 10 □ Yes
9a.	If yes , when did you last give birth? $\frac{DDD}{D}_{12} = \frac{DDD}{D}_{13} = \frac{DDDD}{D}_{14} = DDDDDDDDDDDDDDDDDDDDDDDDDDDDDDDDDDD$
9b.	How many live births have you had?
9c.	How many abortions/miscarriages/still births have you had?
End	ometriosis
10a.	When did you first experience endometriosis symptoms?
10b.	When were you first diagnosed with endometriosis by a physician?    M   M   20   Y   Y   Y   Y   Y   Y   Y   Y   Y

f I

Supporting document SOP BMT 01.09 – Doc 5002.02 – Effective date 21.03.2017

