## III List of potential prognostic factors for primary outcomes

Primary Outcome	Predefined Potential Prognostic Factors
Anemia	EMT user type at follow-up, age, history of anemia, history of bleeding disorders
Depression	EMT user type at follow-up, age, family and personal history of depression, use of Antidepressants/SSRI, severity of pain
Treatment Failure	EMT user type at follow-up, age, family and personal history of depression, current/worsening depression, severity of pain

Supporting document SOP BMT 01.09 – Doc 5002.02 – Effective date 21.03.2017

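### Diagnosis classification at entry stratifies the primary-outcome tables but is in no anemia or depression adjustment set, so any confounding of the DNG vs OAED hazard ratio by it would remain

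*SAP*

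**What the plan says.** **Where the factor is collected and used.** The physician part of the baseline questionnaire (SAP Appendix I, question 3) asks "How would you classify your patient's endometriosis" and offers two answers: symptoms only, or confirmed by surgery or laparoscopy. SAP 6.2.2 defines the item as a subgroup. SAP 5.3.2 lists it as the third stratifying factor for the primary and secondary outcomes: "Diagnostic classification: Diagnosis confirmed by surgery vs. diagnosis based on clinical symptoms". SAP section 8 repeats this for the incidence tables: "The analysis of the primary outcomes (Section C1) is stratified by country, EMT user type and diagnosis classification".

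**Where it is absent.**

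| Place | Anemia | Depression |
|---|---|---|
| SAP 5.4.2 | "Age, history of anemia, history of bleeding disorders" | "Age, family and personal history of depression, use of Antidepressants/SSRI" |
| SAP Appendix III | "EMT user type at follow-up, age, history of anemia, history of bleeding disorders" | "EMT user type at follow-up, age, family and personal history of depression, use of Antidepressants/SSRI, severity of pain" |
| Section D results shells | Table D-1.1.2 footnote: "Adjusted for age, history of bleeding and history of anemia" | D-2 has no shell and no footnote |

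The proposed covariates in protocol section 11 do not include it for either outcome. That section does propose previous surgical treatment, but only for treatment failure.

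**Related provisions.** SAP 5.4.2 leaves the final covariate decision to the SMAC. Protocol section 11 keeps the list to established risk factors because few events are expected, and promises alternative analyses with other baseline risks without naming them. SAP 5.4.2.1 calculates crude and adjusted hazard ratios. SAP 5.2 compares the upper confidence limit with a margin of 2. Neither document says which of the two ratios is compared.

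**The concern.** Treatment is chosen by the physician, and there are no medical entry criteria. Women diagnosed on symptoms alone are enrolled alongside women with surgical confirmation. Diagnosis class is fixed before treatment and could plausibly be related both to the drug prescribed and to the outcome. It may mark severity, or it may separate endometriosis from other causes of bleeding or low mood. If both links exist and the mix differs between cohorts, part of the ratio compared with 2 reflects diagnosis rather than drug.

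The Section C strata do not deal with this. They give incidence rates within each diagnosis class, whereas the conclusion rests on one pooled DNG vs OAED ratio. Section D plans no version of that ratio stratified by or adjusted for diagnosis class. Among the three stratifying factors, user type is a listed cofactor in the SAP and country is named as a candidate in the protocol. Diagnosis class is the only one never named as a candidate for adjustment, and no reason is given.

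**Working it through.** **Step 1. Reproduce the planned size.** Inputs from SAP Tables 2 and 3: one-sided alpha 0.0083, power 90%, margin 2, incidence 0.01 per woman-year in both cohorts, and 2:1 exposure (8,400 and 4,200 women-years).

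Events = (z_α + z_β)² / [(2/3)(1/3)(ln 2)²] = (2.395 + 1.282)² / (0.2222 × 0.4805) = 126.6, rounded up to 127.

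127 / 0.01 = 12,700 women-years, which splits into 8,467 and 4,233. With DNG at 10% of exposure the total is 84,667. The plan gives 8,400, 4,200 and 84,000, so it reproduces within 1%. The planned figures correspond to 84 + 42 events and SE(ln HR) = √(1/84 + 1/42) = 0.189. Non-inferiority then needs an observed hazard ratio below exp(ln 2 − 2.395 × 0.189) = 1.27.

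**Step 2. Effect of leaving out a two-level factor.** Let p1 and p0 be the shares of surgical diagnosis in DNG and OAED, and G the surgical-to-clinical rate ratio for the outcome. To a close approximation with rare events, the hazard ratio is multiplied by

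B = [1 + p1(G − 1)] / [1 + p0(G − 1)].

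The documents give none of p1, p0 or G. The values below are assumptions: p1 = 0.4, p0 = 0.6 or 0.8, and G from 0.5 to 2. The range covers both directions, because more events in the surgical group (severity) and more in the clinical group (other causes) are both conceivable.

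| G | B, p0 = 0.6 | B, p0 = 0.8 | True HR 2.0 appears as |
|---|---|---|---|
| 0.5 | 0.80/0.70 = 1.14 | 0.80/0.60 = 1.33 | 2.29 to 2.67 |
| 0.8 | 0.92/0.88 = 1.05 | 0.92/0.84 = 1.10 | 2.09 to 2.19 |
| 1 | 1.00 | 1.00 | 2.00 |
| 1.25 | 1.10/1.15 = 0.96 | 1.10/1.20 = 0.92 | 1.91 to 1.83 |
| 2 | 1.40/1.60 = 0.88 | 1.40/1.80 = 0.78 | 1.75 to 1.56 |

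If p1 = p0, B = 1 for every G. Swapping the two shares inverts B.

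**Step 3. What this would do to the test.** Take 42 OAED events and 84 × (apparent HR) DNG events, SE = √(1/DNG events + 1/42), and P(upper limit < 2) = Φ[(ln 2 − ln apparent HR)/SE − 2.395].

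- True HR 2, G from 1.25 to 2: the chance of wrongly showing non-inferiority rises from the nominal 0.8% to between 1.6% (apparent HR 1.91, SE 0.173) and 16% (apparent HR 1.56, SE 0.177).
- True HR 2, G from 0.8 to 0.5: the same chance falls to 0.4% or less.
- True HR 1, G from 0.8 to 0.5: power falls from 90% to between 86% (apparent HR 1.05) and 44% (apparent HR 1.33).

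Steps 2 and 3 treat the model as otherwise unadjusted. Part of any imbalance may already be taken up by age, history of anemia and bleeding disorders, or history of depression and antidepressant use.

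**The case against.** The strongest reply is that confounding needs two links, and the documents establish neither. Nothing in them ties diagnosis class to drug choice, or to the incidence of anemia or depression. This stands. A reader might infer that the planned ratio is confounded, or that it is biased in favor of DNG. Neither reading is supported, and the idea that symptom-only diagnoses include other causes of bleeding or low mood implies G below 1, which with the shares assumed above works against DNG.

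Some of the mechanism is also already limited. A confirmed anemia must have no obvious explanation, or none beyond endometriosis-related bleeding, and cases are adjudicated blind to treatment. For depression, severity of pain is a potential covariate in Appendix III, and the protocol introduction reports little correlation between disease extent and pain severity. This makes a large effect less likely but does not rule one out.

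The covariate list is deliberately short and not closed. The SMAC decides, and the protocol promises alternative analyses. That provides a route to the change, but the SAP names no such analysis and Section D has no shell for one. The small-event argument does not apply to a two-level stratum, which adds no regression coefficient.

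Rate ratios by diagnosis class could be worked out from the Section C tables, and country is missing from the SAP lists too. Both are true. However, a derived rate ratio would not carry the other covariates and is not planned. The point about diagnosis class does not depend on its ranking above country.

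**Conclusion.** The omission is real. A pre-treatment item that is on the baseline form and is a stratifying factor for the primary outcomes appears in no adjustment set for anemia (SAP 5.4.2, Appendix III, Table D-1.1.2 footnote) or depression (SAP 5.4.2, Appendix III). Stratum-specific incidence rates do not adjust the pooled ratio. Any confounding by diagnosis class would remain, and its existence, size and direction cannot be known from the documents.

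Under the assumed shares and rate ratios, the multiplier on the hazard ratio runs from 0.78 to 1.33, with 1.00 if the factor is balanced or has no effect. It should be read as a sensitivity range, with covariates already in the model ignored.

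Two further inferences go too far. The Table D-1.1.2 footnote might be read as covering depression, but it concerns anemia only. The adjusted ratio might be taken as the one that decides non-inferiority. Protocol section 11 leans that way by saying confounders will be built into the model, but neither document states it. The low cost of the change, more than any demonstrated bias, is the reason to make it.

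**What to change.** - Stratify the adjusted DNG vs OAED Cox models in Sections D-1 and D-2 by diagnosis classification at study entry, with separate baseline hazards and a common drug effect.
- Take the change through the SMAC, and update the SAP 5.4.2 table, Appendix III and the Table D-1.1.2 footnote. Give D-2 a matching footnote.
- State that the adjusted hazard ratio is the one whose upper limit is compared with 2.

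The cost is SAP wording and one stratum term per model, using data already collected. The downside is small: women without a recorded classification need a missing stratum, and there may be a slight loss of precision. No sample-size figure changes.
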